Predicting Treatment Response to Memantine in Autism Spectrum Disorder using MR Spectroscopy

Protocol 1

Version 7

March 8, 2017

Institution: University of Missouri

Principal Investigator: [name], M.D.

Co-Investigator: [name]

Abstract

Memantine, an N-methyl-D-aspartate receptor antagonist, has been explored as a possible therapeutic agent that reduces the excitatory (glutamate) – inhibitory (gamma amino-butyric acid, GABA) imbalance in autism pathology and improves social and communication deficits. While some studies have shown positive results, a large clinical trial failed to show benefit possibly because different subsets of autism responded differently to the treatment. We propose a pilot, exploratory, clinical follow-on study using proton magnetic resonance spectroscopy (¹H-MRS) to determine whether baseline glutamate/GABA levels in certain regions of the brain may help predict treatment response to Memantine in autistic subjects. At study onset, subjects will be assessed on the behavioral scales such as the Aberrant Behavior Checklist and Clinical Global Impressions scale, followed by MRS imaging. Memantine treatment will be started post imaging. Assessment measures will be repeated at week 12 during treatment. Glutamate and GABA levels in brain regions will be correlated to improvements on assessment measures. We expect higher glutamate and/or lower GABA levels in the anterior cingulate cortex at baseline in responders to memantine. If our hypotheses are confirmed, we will have established a relevant neural biomarker to predict treatment response to memantine with important implications for clinical care including improving accuracy of individual prognosis and individualizing treatments.

Objectives

Specific Aim 1: We propose a pilot, exploratory, clinical follow-on study using proton magnetic resonance spectroscopy (¹H-MRS) to examine whether the following measures can be used to predict treatment response to memantine in ASD:

- (a) Glx and/or GABA and the Glx/GABA ratio in the anterior cingulate cortex,
- (b) Glx levels in the dorsolateral prefrontal cortex and the cerebellum
- (c) Markers of neuronal integrity, N-acetyl aspartate (NAA), myo-inositol, choline and creatine/phosphocreatine levels in the anterior cingulate, dorsolateral prefrontal cortex and cerebellum

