The anterior cingulate cortex, dorsolateral prefrontal cortex and the cerebellum have been have been chosen as ROIs due to known atypical glutamate and GABAergic profiles in these regions associated with ASD^{2,5,7,9,25–32}. The approach of limiting to selected ROIs has been adopted in order to ensure patient comfort during the imaging process by reducing the time spent in the scanner. Since altered levels for markers of neuronal integrity, such as NAA, choline, creatine/phosphocreatine and myoinositol have also been reported in ASD, ^{3,5,6,9,29,33–36} we will be mapping these biochemicals as well in order to explore their effect on treatment response. Resting state functional connectivity will also be analyzed for possible association with treatment outcome prediction since a previous study from our lab has shown a link between alterations in resting state

cerebrocerebellar connectivity, excitatory-inhibitory ratio in the cerebellum and behavioral outcome in ASD using MR spectroscopy²⁶.

Study Design

We propose to enroll 25 subjects with ASD for this pilot, exploratory study who are interested in starting memantine off-label as a clinical follow on. Glutamate concentration variations with MRS have been successfully reported with this sample size by Page et al., 2006³⁷. Subjects will be recruited from Pl's clinic at the Thompson Center for Autism and Neurodevelopmental Disorders at the University of Missouri. The Thompson Center (TC) is one of the leading sites for recruitment within the Autism Treatment Network with more than 375 participants recruited since 2008. Our group and other TC researchers have successfully recruited imaging patients from this resource for multiple federally funded research projects. We have preliminary behavioral data on 15 ASD patients currently on memantine treatment showing mixed responses.

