sample of 5 controls. Peaks from GABA, Glx, and glutamate are clearly discernible. [name] will supervise these scans. Our previous studies found that subjects with ASD are compliant with the ~60 minutes acquisition time. ¹H-MRS data analysis was detailed previously²⁹. Briefly, we use LCModel to quantify absolute GABA, Glx, and glutamate concentrations and other metabolites mentioned. LCModel-concentrations are corrected for partial brain tissue volume within voxel using a software written in Matlab software (2013a Mathworks, Natick, MA) and segmented structural images (SPM8, London, UK). For specific aim 1(b) and (c), spectroscopy voxels will be placed over the dorsolateral prefrontal cortex and cerebellum and concentrations of glutamate/glutamine, N-acetyl aspartate (NAA), myo-inositol, choline and creatine/phosphocreatine levels will be extracted. Resting state functional connectivity data will also be acquired during the imaging session for specific aim 2.

Following the imaging session, subjects will be started on memantine, starting at 5 mg/day doses to be titrated up 20 mg/day based on response and tolerability, for a period of 12 weeks as part of clinical care.

Follow-up assessments:

Subjects will be assessed after week 12 of memantine administration using the same clinical testing battery used prior to drug administration. We will also use an additional scale to determine improvement in symptoms: Clinical Global Impression – Improvement (CGI-I) scale. The CGI-I scale assesses the patient's improvement on a scale of 1-7 where 1 represents very much improved and 7 represents very much worse when compared to baseline (before initiation of memantine). The reference for baseline severity will be derived from the CGI-S score obtained before initiation of memantine. Subjects who score 1-3 on the CGI-I will be considered responders while those who score 4-7 will be considered non-responders, a technique commonly used to categorize responders vs. non-responders in treatment response monitoring studies ^{40,47,48}. Subjects will be assessed for improvements on the SRS, GSOM, TLC and each of the 5 subscales of the ABC described earlier. Additionally, research staff will review ASD subject medical records to gain a better understanding of clinical benefit from drug administration. This will include physician clinical notes and any standardized assessments of clinical/behavioral improvement.

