Information produced by this study will be stored in a locked cabinet or secure server in the PI's offices in Galena Hall. Each subject will be assigned an anonymous study specific code. The code key will be kept on a separate secure server. Information contained in records will not be given to anyone not associated with the study without written consent, except as required by law.

Analyses:

Using data from the MR spectroscopy study performed at baseline, the means (SD) for each of the different compounds – GABA (in the anterior cingulate cortex only), Glx, NAA, choline, myo-inositol, creatine and phosphocreatine - measured from the different ROIs mentioned above will be analyzed for differences in responders vs. non-responders to memantine treatment. The ratio of Glx/GABA from the anterior cingulate will also be included in all analyses to explore effects of the excitatory-inhibitory ratio of the region on treatment response. Means (SD) of the different compounds and Glx/GABA ratio will also be correlated to CGI-I and changes in SRS scores and GSOM and ABC measures for each ROI to explore additional specific differences using Spearman's correlation coefficients. A significance level of 0.05 will be used. Since demographic factors such as age and gender are known to influence the results of MR spectroscopy studies ⁴⁹, demographic factors will be included in the analysis to account for the associated changes in metabolite concentrations.

For resting state functional connectivity, we will extract time series from the regions of interest and correlation analyses will be carried out. The strength of functional connectivity between the regions will then be correlated to changes on scores in the battery of clinical tests to determine whether resting state functional connectivity might have a role in treatment response to memantine.

Hypothesis and Expected Results: We hypothesize that the best responders will have higher concentrations of glutamate/glutamine and reduced levels of GABA in the anterior cingulate cortex at baseline. Consistent with previous studies, we also expect to see increased glutamate/glutamine levels in the dorsolateral prefrontal cortex and cerebellum^{38,39} and increased

resting state functional connectivity in cortical networks⁵¹ that will be related to treatment response. Data from this pilot, exploratory study will be used to derive power for a larger, follow up study.

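### Aims 1(b), 1(c) and 2 involve about 150–177 tests at an unadjusted 0.05 in 25 subjects; if no association is real, about 7.5–8.9 significant predictor–outcome associations are expected by chance

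*Combined protocol and SAP*

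**What the plan says.** Objectives, Aim 1(b) concerns "Glx levels in the dorsolateral prefrontal cortex and the cerebellum". Aim 1(c) concerns "Markers of neuronal integrity, N-acetyl aspartate (NAA), myo-inositol, choline and creatine/phosphocreatine levels in the anterior cingulate, dorsolateral prefrontal cortex and cerebellum". Aim 2 concerns resting-state connectivity among the same three regions.

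The Analyses section plans a responder versus non-responder comparison for each compound in each region. It adds Spearman correlations of each compound with CGI-I and with changes in SRS, GSOM and the ABC. It lists the compounds other than GABA as "Glx, NAA, choline, myo-inositol, creatine and phosphocreatine", so creatine and phosphocreatine may be one marker or two. For Aim 2 it says: "The strength of functional connectivity between the regions will then be correlated to changes on scores in the battery of clinical tests".

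Follow-up assessments describes the outcomes: "Subjects will be assessed for improvements on the SRS, GSOM, TLC and each of the 5 subscales of the ABC described earlier".

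The only threshold is "A significance level of 0.05 will be used". It stands in the metabolite paragraph; the connectivity paragraph gives none. The documents name no primary predictor, primary outcome, test family or multiplicity adjustment.

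Study Design states: "We propose to enroll 25 subjects with ASD for this pilot, exploratory study". The sample size rests on precedent: "Glutamate concentration variations with MRS have been successfully reported with this sample size". Hypothesis and Expected Results puts anterior cingulate Glx and GABA first. It also states expectations for the dorsolateral prefrontal cortex, the cerebellum and connectivity, and says the data will be used to power a larger study.

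**The concern.** The lead hypothesis, on anterior cingulate Glx and GABA, is a separate matter, and no test of those two or of their ratio is counted here. What remains is a broad screen of many markers against many outcomes in a small sample, with one per-test threshold and no statement of how many positive results chance alone would produce.

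At stake is the reading of the results. If several markers or links reach 0.05, the plan gives no means of telling a real signal in the prefrontal cortex, the cerebellum, the neuronal-integrity markers or connectivity from the expected background. The results also have a further use: effects picked out because they crossed 0.05 at n = 25 tend to be overestimates, and a follow-up study powered on them would tend to be too small or to pursue noise.

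**Working it through.** The documents give no test count, error rate or power figure to reproduce, so the count is built from the text.

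**Inputs**
- Aim 1(b): Glx in 2 regions = 2 predictors (Objectives).
- Aim 1(c): 4 markers × 3 regions = 12 predictors (Objectives), or 5 × 3 = 15 if creatine and phosphocreatine are analysed separately (Analyses).
- Aim 2: 3 pairs of regions = 3 predictors.
- Tests per metabolite predictor: 1 responder contrast + 8 correlations (CGI-I, SRS, GSOM, 5 ABC subscales) = 9. The five subscales come from Follow-up assessments; Analyses says only that ABC measures are used.
- Tests per connectivity pair: SRS, GSOM, TLC and 5 ABC subscales = 8 change scores.

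**Test count and expected chance hits.** The expected number is 0.05 × number of tests when no association is real. Correlation between tests does not change it.

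| Aim | Tests | Expected at 0.05 |
|---|---|---|
| 1(b) | 2 × 9 = 18 | 0.9 |
| 1(c) | 12 × 9 = 108, or 15 × 9 = 135 | 5.4, or 6.75 |
| 2 | 3 × 8 = 24 | 1.2 |
| Total | 150, or 177 | 7.5, or 8.85 |
| Total without Aim 2 | 126, or 153 | 6.3, or 7.65 |

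**Other readings** (creatine and phosphocreatine as one marker, then as two)
- ABC as one score: 14 × 5 + 3 × 4 = 82; 17 × 5 + 3 × 4 = 97. Expected 4.1–4.9.
- CGI-I added to connectivity: 14 × 9 + 3 × 9 = 153; 17 × 9 + 3 × 9 = 180. Expected 7.7–9.0.
- TLC also added to the metabolite tests: 14 × 10 + 3 × 9 = 167; 17 × 10 + 3 × 9 = 197. Expected 8.4–9.9.
- GSOM as five domains: 14 × 13 + 3 × 12 = 218; 17 × 13 + 3 × 12 = 257. Expected 10.9–12.9.

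**Distinct predictors flagged.** There are 2 + 12 + 3 = 17 predictors, or 2 + 15 + 3 = 20. If tests were independent, the expected number with at least one hit is 14 × (1 − 0.95⁹) + 3 × (1 − 0.95⁸) = 6.2 of 17, or 17 × (1 − 0.95⁹) + 3 × (1 − 0.95⁸) = 7.3 of 20.

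**Effect of dependence.** These are null simulations at n = 25 with 1,500 runs per setting, using Spearman tests plus a t-test for CGI-I 1–3 versus 4–7. The correlations, equal among predictors and among outcomes, are assumptions.

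| Tests | Assumed correlation | Mean hits | 5th / 50th / 95th percentile | At least one hit | Mean distinct predictors flagged |
|---|---|---|---|---|---|
| 150 | 0 | 7.55 | 3 / 7 / 13 | 99.9% | 6.0 |
| 150 | 0.3 | 7.66 | 2 / 7 / 15 | 99.5% | 5.6 |
| 150 | 0.5 | 7.54 | 1 / 6 / 21 | 95.4% | 4.7 |
| 177 | 0 | 9.00 | 4 / 9 / 14 | 100% | 7.2 |
| 177 | 0.3 | 8.87 | 3 / 8 / 17 | 100% | 6.4 |
| 177 | 0.5 | 8.81 | 1 / 7 / 23 | 97.6% | 5.5 |

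At correlations up to 0.6 the number of distinct predictors flagged falls to about 4.3. Dependence leaves the mean alone but widens the spread.

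**Effect of Benjamini–Hochberg within each aim.** In null simulations with correlations of 0 to 0.6, the chance of any false claim across the three aims was 12–17% at q<0.05 and 20–30% at q<0.10.

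**The case against.** The strongest reply is that the study calls itself a pilot and exploratory in the Abstract, Objectives and Study Design. Analyses says the correlations, which are 8 of the 9 tests per metabolite, serve to explore further differences, and it asks only whether connectivity might play a part. The firm language about having established a biomarker follows the anterior cingulate hypothesis, which is outside this count. Whether to adjust an openly exploratory screen is partly a matter of judgement, and adjustment costs power where leads are wanted.

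Much of this stands. It lowers the weight of the point and argues against letting a q-value decide which leads survive. It does not dispose of the point: the aims are framed as prediction of response, the plan states expectations for the other regions and for connectivity, and the data are to power a follow-up. A label does not tell the reader how many of the reported hits chance would supply.

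Two details of the count are also open. Applying 0.05 to Aim 2 is an inference, and 150–177 allows only for the creatine/phosphocreatine ambiguity. Even the smallest count considered, 82, gives about 4 expected chance hits.

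A reader might infer that 7 to 9 separate predictors would be falsely declared. The figures do not support that: 7.5–8.9 counts predictor–outcome associations, and one predictor can contribute several.

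**Conclusion.** The concern holds in a limited form. On the most direct reading, Aims 1(b), 1(c) and 2 comprise 150–177 tests, with 7.5–8.9 nominally significant associations expected by chance and about 4–7 of 17–20 distinct predictors flagged. Without Aim 2 the figures are 126–153 tests and 6.3–7.7 associations.

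The expected numbers assume that no association in these aims is real. The number of distinct predictors and the chance of at least one hit also depend on the assumed correlations. Sidedness and the test for the group comparison are not named, but neither affects the expectation.

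It would go too far to conclude that any positive result from these aims must be false, or that the plan offers them as confirmatory. The documents say neither. The defect is that nominal hits would be reported against a prediction question with nothing to calibrate them.

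**What to change.** In Analyses, for Aims 1(b), 1(c) and 2:
- Keep every nominal p-value and every effect estimate, with confidence intervals.
- Print beside each p-value a Benjamini–Hochberg q-value computed within its aim.
- Settle the outcome list (ABC subscales or one score, GSOM total or domains, where TLC and CGI-I enter, creatine and phosphocreatine together or apart). Then state the number of tests and expected chance hits per aim. On the direct reading these are 18 and 0.9 for Aim 1(b), 108–135 and 5.4–6.75 for Aim 1(c), and 24 and 1.2 for Aim 2.
- State the significance level for Aim 2.
- Describe results significant only at nominal 0.05 as hypothesis-generating, not as predictors of response.

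Do not make q<0.10 a condition for carrying a lead forward.

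The cost is a few sentences and no new data. The downside is that fewer results can be called significant. For one true correlation of 0.5 (assumed, with outcomes correlated 0.5), detection falls from about 69% nominally to about 39% at q<0.10 in Aim 2, and from about 68% to about 19% in Aim 1(c) with 12 markers. That loss is why the q-value should inform the reading and not act as a gate. No result drops out of the report.
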